In RDS, each participant (seed) will be asked to refer up to three other individuals in their social network who meet study inclusionary criteria. Seeds will be compensated twenty (\$20.00 dollars) per each eligible participant who enrolls in the study. This procedure will be followed for three legs for each initial participant (seed) at which point a new seed will begin in effort to avoid skewing the sample.

In addition to the recruitment strategies used for Aim 1, we will be recruiting using telephone outreach calls to previous community gatekeepers in the urban areas and extant participant's pipeline. The electronic and telephone calls, and voicemails outreach approach may be a temporary measure due to the 2019-2020 Coronavirus Pandemic.

Presently, we will be conducting recruitment remotely. Additionally, we will continue recruiting vial local radio stations, social media, online resources and different technology venues available to reach the urban and the semi-rural community. These recommendations will be followed for the safety of participants, staff and the community.

8) Study Timelines*

The timeline shown in Table 2 is the intended timeline. Some of the activities may not be completed within the proposed time.

Aim 1. After the study protocol has been approved by the IRB. Participants will be recruited for the focus groups and interviews. Focus groups and interviews will be facilitated by trained protocol personnel and transcription will commence immediately after data collection as shown in Table 2.

Aim 2. After potential participants are identified and screened for eligibility, a meeting will be scheduled to complete informed consent procedures and baseline assessments. Fatherson dyads interview time and dates will be scheduled simultaneously and will be interviewed separately in order to maintain confidentiality. Once dyadic groups are interviewed, they will be entered into the study in waves of 20 dyads to avoid delays between recruitment, randomization, and intervention delivery. Intervention sessions will be scheduled based on participants groups availability (6-8 fathers will be invited to participate per group session for the control and the intervention). Control and intervention groups will be conducted within the same time frame (participants eligibility includes being available for the intervention group and the control group).

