Focus groups and interviews will be conducted by bilingual trained protocol personnel, audio-recorded, and transcribed verbatim for analysis (in the language they were conducted) using N-vivo. For each focus group, participants will determine whether the focus groups will be conducted in English or Spanish. We anticipate that adolescent groups will prefer English and adults will prefer Spanish. Interviews (40-60 minutes) will be conducted in English or Spanish according to the participant's preference. A semi-structured in-depth interview guide will be developed based on previous formative research, using questions from the focus groups and focus group findings.

The data from Aim 1 will provide the foundation for adapting and pre-testing the HoMBRES de Familia intervention. A subsequent quantitative evaluation of the adapted intervention's efficacy (Aim 2) will be completed via a 2-arm randomized control trial (RCT) with a sample of 160 father-son dyads (N=320)

Aim 2:

The 2-arm RCT will test the efficacy of the adapted intervention with a sample of 160 father-son dyads (N=320). After potential participants are identified and screened, a

Page 8 of 23 Revised: March 23, 2020

IRB Study Number:

Version HoMBRES de Famlia (HoMBRES) #1

meeting will be scheduled to complete informed consent procedures and baseline assessments. Father-son dyads will be entered into the study in waves of 20 dyads to avoid delays between recruitment, randomization, and intervention delivery. Father-son dyads will be randomized into the intervention or control condition using the computer software RANDI2. Randomization will be done using the dyads ID after pre-test. Father-son dyads will be randomized into the intervention (HoMBRES) or control condition. Adolescents will only be expected to participate in baseline and 6-month follow up assessments, as the intervention program is solely parent-based.

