A locator form completed by each participant father during the baseline assessment will guide initial attempts to contact participants. This screening form will contain two or three local phone numbers associated with the participant (father), the address where the participant lived when interviewed, email address, social media contact information. We will also use the following retention strategies as needed: (1) send a letter to participants seeking their continuous participation in the study; (2) contact participants by email; (3) conduct home visits if we cannot reach participants by phone or email; (4) make up to monthly phone calls to ascertain if there are changes in contact information or address; (5) use corroborative contact sources (from locator form); and (6) maintain routine contact with participants through project newsletters or cards for birthdays or US/Latin American holidays. If participants cannot be reached by the above methods, we will use online phone directories, Internet search engines, and social networking sites to locate updated contact information. Only adults will be searched/contacted in this manner. A combination of postal mail, email, and text reminders and confirmation calls will help minimize missed appointments.

HoMBRES Intervention. Due to the outlined measures above, the intervention HoMBRES will consist of four sessions remotely facilitated via a well-tested video platform accessible by a link sent to the participants' telephone, computer, tablet or IPad (approximately 1.5 hours each session) during the period of social distancing, and perhaps beyond if we find that the remote sessions are working well. Intervention videos will be followed up with a telephone call to respond to any questions participants may have about the sessions and clarify (if needed) the material covered in the videos via telephone or text messages. Staff will schedule the times when participants will watch the videotaped sessions in order to be available for their questions. Topics covered across the modules/ sessions are shown below. Participants will also be provided with a resource application (app) and online link with a list of community service providers related to substance abuse, HIV/AIDS, and violence.

Hombres Intervention modules:

Module1:

Program introduction/ Parental cultural influence on adolescents Module

2:

- HIV prevention and STIs and sexual behaviors

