- The role of parents as educators/ the role of educators in the community

Module 3:

- Talking to your son about sexual practice and relationships
- Alcohol and drug prevention

Module 4

- Domestic violence prevention/Father as educator
- Class Review

Page 9 of 23 Revised: March 23, 2020

[figure not shown]
IRB Study Number:

Version HoMBRES de Famlia (HoMBRES) #1

Parents feedback and evaluation

Health Promotion Control. Fathers randomized to the control group will receive a Health Promotion /Diabetes Prevention intervention guided by the CDC recognized Prevent2 program.64 The diabetes prevention lifestyle program will be provided to the fathers in a secured link or website platforms accessible from a phone, computer, tablet or IPad. The session will be 1.5 hours approximately. Session content will focus on the importance of physical activity, healthy eating, and maintaining a healthy weight. Fathers will receive information to share with their participant sons and other family. The intervention will not include discussion on SAVA-related factors in the population.

Figure 1. Research Design [Noonly father participants in the interventions]

Assessments. Baseline data will be collected for fathers and sons in both the intervention

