Quantitative Data Analysis Plan In testing the efficacy the HoMBRES de Familia intervention, we will utilize a 2-arm RCT employing intent-to-treat analysis using the initial group assignment, without considering the number of sessions that participants attend. We will run descriptive analyses at baseline for sociodemographic variables including age, country of birth, education, income, and marital status, and assess the differences between intervention group and control group at baseline using t-test for continuous variables and Chi-square test for categorical variables. We will test the efficacy of the intervention on individual outcomes (substance use, family violence, HIV) to examine how each component of the SAVA syndemic was independently impacted. We will use linear mixed model for continuous outcomes and generalized linear mixed model for categorical outcomes at follow-up, while adjusting for baseline measures, sociodemographics, and potential cluster effect among groups in intervention group and father-son dyads.

Page 12 of 23 Revised: March 23, 2020

IRB Study Number: Version HoMBRES de Familia (HoMBRES) #1

13) Provisions to Monitor the Data to Ensure the Safety of Subjects*

All aspects of the Research Project implementation will be governed by Research Project Lead ([name]) with assistance of Project Co-Lead ([name]) or Project Coordinator ([name]) under the monitoring of the Protocol PI ([name], formerly known as [name]). Data quality assurance procedures will be done by a trained staff member. Researchers will monitor and follow-up and report as required suicidality ideation and child as well as elderly abuse. The study will be monitored by the CLaRO Study Monitoring Unit which is based at the UM School of Nursing and Health Studies. The Study Monitoring Unit will (1) verify compliance with regulatory requirements, (2) ensure that the Project Leads and staff (including those at community agencies) are fully informed of regulatory requirements and properly trained to perform the duties assigned, and (3) monitor procedures to prevent errors and minimize protocol deviations that can negatively affect quality of the data collected and compromise human subjects' protection. The project will have a quality assurance (QA) review: prior to initiation, upon conducting baseline procedures with the first wave of study participants; and bi-annually for interim reviews.

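### Should the outcome model carry a term for wave of entry, with allocation balanced inside each wave of 20 dyads?

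*Combined protocol and SAP*

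**What the plan says.** Entry in waves appears twice: in section 8 (Study Timelines, Aim 2), "Once dyadic groups are interviewed, they will be entered into the study in waves of 20 dyads", and in section 10 (Procedures Involved, Aim 2), "Father-son dyads will be entered into the study in waves of 20 dyads to avoid delays between recruitment, randomization, and intervention delivery". Section 10 adds that allocation uses RANDI2 and that "Randomization will be done using the dyads ID after pre-test". The available text gives no allocation ratio, blocking or strata, and does not say whether a wave is randomised as a batch or dyad by dyad. Part of the document between sections 21 and 25 was not available.

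Section 8 also sets the session size, "6-8 fathers will be invited to participate per group session for the control and the intervention", and the timing, "Control and intervention groups will be conducted within the same time frame".

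The outcome model, under Quantitative Data Analysis Plan in section 12, is a linear or generalised linear mixed model fitted "while adjusting for baseline measures, sociodemographics, and potential cluster effect among groups in intervention group and father-son dyads".

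On delivery, section 10 has HoMBRES given remotely "during the period of social distancing, and perhaps beyond if we find that the remote sessions are working well". For the comparator it says "The diabetes prevention lifestyle program will be provided to the fathers in a secured link or website platforms" and sets no end date. Section 21 (Setting) names community venues for Aim 2 and moves Aim 2 to remote procedures during the pandemic.

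**The concern.** Four things invite a challenge.

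- **Wave is in the design but not in the model.** Conditions changed during enrolment. Section 30 refers to participants enrolled before social distancing, and recruitment and assessment then moved to remote methods. Dyads that enter together may therefore resemble one another. If RANDI2 does balance within waves, leaving wave out makes the test slightly conservative. If it does not, single waves can be lopsided.
- **The group effect is written for the intervention arm only**, although section 8 plans groups in both arms. If groups are formed within waves, that term can take up wave variation which both arms share and charge it to one arm, at a cost in power.
- **Wave size and group size seem not to match.** Ten fathers per arm make one group of 10 or two of 5, not groups of 6 to 8.
- **Delivery format after distancing is left open.** If the arms then used different formats, format would become part of the arm contrast.

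**Working it through.** **Inputs from the protocol.** 160 dyads, waves of 20, groups of 6 to 8 fathers, and the model terms quoted above. 160/20 = 8 waves.

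**Assumptions, because the documents give no figures.** 1:1 allocation, simple unless stated as balanced; two-sided alpha 0.05; effect d = 0.45 SD; no dropout; one continuous outcome per dyad. Let v be the wave share of the variance left after baseline adjustment, shown at 0, 2, 5 and 10%. The protocol gives no power calculation to reproduce.

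**1. Lopsided waves.** Under simple allocation, P(13:7 or worse) = 2 × P(Bin(20, 0.5) ≥ 13) = 0.263 per wave. This is chance imbalance, unrelated to outcome.

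**2. Information on the treatment effect.** For one comparison, I = n1 × n0/(n1 + n0).

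- Simple allocation, no wave term: expected I = (160 − 1)/4 = 39.75.
- All 8 waves 10:10, wave term fitted: 8 × (10 × 10/20) = 40.
- Four waves balanced, wave term fitted: 4 × 5 + 4 × 4.75 = 39.
- No wave balanced, wave term fitted: 8 × (20 − 1)/4 = 38.

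A fixed wave term removes v from the residual variance, so the relative information is (I/39.75)/(1 − v). Break-even is v = 1 − I/39.75: 1 − 38/39.75 = 4.4% with no balance and 1 − 39/39.75 = 1.9% with half the waves balanced.

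**3. Power without a group term.** Power ≈ Φ(0.45 × √(I/(1 − v)) − 1.96). As planned, the residual keeps the wave variance, so power is Φ(0.45 × √39.75 − 1.96) = Φ(0.877) = 81% at every v. For all waves balanced at v = 10%, it is Φ(0.45 × √(40/0.9) − 1.96) = Φ(1.04) = 85%. Simulation with 40,000 trials per cell gave:

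| Allocation and model | v = 0 | 2% | 5% | 10% |
|---|---|---|---|---|
| Simple, no wave term | 81% | 81% | 81% | 81% |
| 8 waves balanced, fixed wave term | 81% | 81% | 83% | 85% |
| 4 waves balanced, fixed wave term | 80% | 81% | 82% | 84% |
| None balanced, fixed wave term | 79% | 80% | 81% | 83% |

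**4. Type I error if balanced but wave omitted.** 2 × (1 − Φ(1.96/√(1 − v))) = 5.0, 4.8, 4.4 and 3.9%. The error is on the safe side. Under simple allocation it stays near 5%.

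**5. With the intervention-arm group term.** This simulation takes groups as formed within waves and the true group variance as zero.

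| Configuration | v = 0 | 2% | 5% | 10% |
|---|---|---|---|---|
| One group per wave: simple, no wave term | 78% | 77% | 74% | 69% |
| One group per wave: all balanced, fixed wave term | 76% | 76% | 78% | 80% |
| Two groups per wave: simple, no wave term | 79% | 79% | 78% | 77% |
| Two groups per wave: all balanced, fixed wave term | 79% | 80% | 82% | 83% |

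With one group per wave, type I error for the plan as written was 4.3, 3.9, 3.3 and 2.6%, so it is again conservative.

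**6. Group fit.** n fathers fill k groups of 6 to 8 if 6k ≤ n ≤ 8k. Within one wave of 20, both arms fit only at 6:14, 7:13 or 8:12. Section 8 does not confine a group to a wave: sessions are scheduled on participants' availability. Over the trial, 80 fathers per arm make exactly 80/8 = 10 groups of 8. The mismatch exists only under a nesting rule that the protocol does not state.

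**7. Delivery passages side by side.** Section 8 has groups in both arms. Section 10 has HoMBRES remote for now, with a later decision reserved, and the control by link. Section 21 has Aim 2 remote during the pandemic, which can cover the control link as well. No section plans a different format for each arm.

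**The case for a change.** The strongest case is step 5. If groups sit inside waves and v is 10%, power is 69% as written against 80% with balance and a wave term. Conditions did change during enrolment, so some wave variation is plausible, and the remedy looks cheap: one software setting and one sentence in the model.

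The arithmetic stands, but three things weaken it. First, the 69% cell needs v = 10% after baseline adjustment, which no document supports, and about 10 fathers in each intervention group, which is outside the planned 6 to 8. The two-group case has about 5 fathers each, also outside the range, and its gap at v = 10% is 83 − 77 = 6 points. Second, at v = 0 with one group per wave, a fixed wave term loses about 2 points if all waves are balanced, 3 if half are and 5 if none are. Some dyads enrolled before distancing, and waves already allocated cannot be rebalanced, so full balance may be out of reach. Third, much of that gap comes from writing the group term for one arm. That is a question of which arms hold groups, and a wave term does not settle it.

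It is also fair that the text never says how RANDI2 is configured and leaves the format after distancing open. Both are missing detail. Neither makes the comparison as planned invalid.

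**Conclusion.** No change follows. The comparison of arms is unbiased and its test is valid, or slightly conservative, whether or not RANDI2 balances by wave. This rests on random allocation and on both arms running in the same time frame.

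A fixed wave term is a trade-off on an unknown quantity. Without a group term, and with all waves balanced, it gains about nothing at v of 0 to 2% and about 2 to 4 power points at 5 to 10%. With no balance it loses below v = 4.4%, by about 2 points at v = 0. These figures assume d = 0.45 SD, 160 dyads with no dropout and 1:1 allocation. Leaving wave out is a defensible choice within that range.

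The rest is detail that the team fills in when running the trial: the RANDI2 setting, batch or single randomisation, and how groups are made up. The group-size mismatch disappears once groups may cross waves. The delivery sections should be read together and reconciled on what happens in each arm after distancing. They reserve that decision and do not contradict one another, and the analysis by assigned arm holds whichever way it goes.

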Adverse Events and Serious Adverse Events (AE and SAE): The Project Lead and protocol PI will be responsible for monitoring and reporting and comply with the reporting requirements of the IR B and NIMHD. The Data and Safety Monitoring plan will have required reports will include any adverse events as well as the results of analysis conducted. The PI and Project Lead will ensure that any AE or SAE are timely reported to the IRB.

During the study implementation, we foresee that they may be certain events with the families such as: 1) domestic violence; 2) work contract was terminated and participant has to move to another city; 3) entire family is moving to another estate; 4) father moved out of the home; 4) father was kicked out of home.

Among the Serious adverse events (SAE) we may encounter: 1) physical abuse with partners and adolescents, 2) hospitalization, 3) substance abuse. All assessments conducted by the study's interviewers are opportunities for identifying adverse events if reported by the participant and/or a family member. The educators will be trained to identify AEs and SAEs at session of the intervention and at each interview or assessment points. Additionally, anytime during the study, a participant or his/her family member may report an AE/SAE to their group facilitators/educators. These events will be identified, classified as serious or not, and will be handled in the same manner as AEs/SAEs during the formal assessments.

Study personnel (including peer advocates) will be trained to identify adverse events, and categorize serious adverse events, based on direct reporting during sessions. Upon identification of an adverse event, the team member should notify the study coordinator who will assess the event for seriousness to guarantee that appropriate care and reporting occur within approximately 24 hours. As soon as an adverse event is identified either by querying or direct report, the event will be recorded in the AE log. In addition, the Project Lead ([name]) or Co-Project Lead ([name]) or Project Coordinator ([name]) will be notified of any and all AEs. In both treatment conditions, action may be taken by the peer advocate to respond to non-serious events (e.g., referral to counselor, community program, local agency or hospital). The

Page 13 of 23 Revised: March 23, 2020

IRB Study Number: Version HoMBRES de Famlia (HoMBRES) #1

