Under Aim 3, dissemination of the study findings will be accomplished in close collaboration with the Community Engagement and Dissemination Core of CLaRO (parent NIH contract for this study).

Page 16 of 23 Revised: March 23, 2020

IRB Study Number: Version HoMBRES de Famlia (HoMBRES) #1

Strategies for providing relevant information to the LSFW community: Under Aim 3 dissemination strategies will be performed in areas where LSFWs gather, socialize, and celebrate. In MDC, this includes local flea markets, recreational parks, Latino festivals, health fairs, and places. Dissemination activities will include: (a) Presentations to community stakeholders and service providers involved in addressing substance abuse, family violence, and HIV/AIDS in the local community, and (b) Distributing information to the local community via informational booths at local health fairs and ethnic festivals.

21) Setting

Procedures for Aims 1 and Aims 2 will be provided in private community settings including the COFFO offices as well as the Everglades Community Center and Redland farm camp community center or other locations in the urban, semi-rural areas of Homestead, Naranja and Florida City or other locations within walking distance or short drive of participants homes. During the COVID-19 Pandemic, procedures of Aims 2 will be conducted remotely as described above. Once dyads are interviewed, they will be sent a private link with the video sessions based on the group randomization. This approach will help us avoid delays between recruitment, randomization and intervention delivery. Interventions will be facilitated via a secured link. The webinar style video will be solely available to participants using a private link (ie. Zoom, youtube, powerpoint and other venues available to the participants). These venues can provide privacy and confidentiality.

Incentives for participation will be delivered by money order, electronic cash deposits or payments such as Zelle or another electronic platform preferred by participants. It should be noted that participants in this study are of very limited financial means and may not all have access to platforms used at UM (e.g., Zoom), furthermore, we are trying to use means of communication that participants are accustomed to. We will have to assess their technology and will proceed accordingly, using the UM platforms as first line, but may need to use other means of communication and transmission as per participant access.

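### Session-group clustering is modelled in the intervention arm only, although both arms are planned in groups of 6–8 fathers, so the standard error may be too small

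*Combined protocol and SAP*

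**What the plan says.** Section 12 (Quantitative Data Analysis Plan) specifies linear mixed models for continuous outcomes and generalized linear mixed models for categorical ones, adjusted for baseline measures, sociodemographics and "potential cluster effect among groups in intervention group and father-son dyads". Earlier in that paragraph the analysts are to "assess the differences between intervention group and control group at baseline", so there the term intervention group names one of the two arms. The analysis is "intent-to-treat analysis using the initial group assignment, without considering the number of sessions that participants attend".

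Section 8 (Study Timelines, Aim 2) describes the grouping: "6-8 fathers will be invited to participate per group session for the control and the intervention". It adds: "Control and intervention groups will be conducted within the same time frame".

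The delivery sections are less clear about groups. Section 10 (Health Promotion Control) states: "The diabetes prevention lifestyle program will be provided to the fathers in a secured link or website platforms". Section 21 (Setting) says that during the pandemic, once dyads have been interviewed, "they will be sent a private link with the video sessions based on the group randomization". Section 10 also has the intervention sessions delivered by video link while social distancing lasts, and possibly afterwards.

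**The concern.** The design groups fathers in both arms, but the model has a group term for one arm only. A model with clustering in one arm (a partially nested model) suits a trial whose control participants are not grouped. Section 8 describes a grouped control arm, and no section available for review argues that control fathers are independent.

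If control groups have an ICC above zero, the control mean is less precise than the model assumes. The standard error of the arm difference is then too small, confidence intervals are too narrow and the type I error can exceed its nominal level. In the linear model the effect estimate itself is not biased. The rule covers every outcome analysed this way. The plan also does not say how a dyad without a session group enters the model.

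**Working it through.** **Inputs from the documents.** 160 dyads (section 6); 6–8 fathers per session group in both arms (section 8); group term in the intervention arm only (section 12). The documents give no ICC, significance level or sample-size calculation, so there is no figure to reproduce.

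**Assumptions.** 1:1 allocation (160/2 = 80 fathers per arm), two-sided 5% test, ICC 0.02–0.10, one continuous outcome per dyad, equal total variance in both arms.

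**Formula.** Let m be the group size and g the share of control fathers who meet in groups.

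- Design effects: DE_I = 1 + (m − 1) × ICC_I and DE_C = 1 + g × (m − 1) × ICC_C.
- The true variance of the arm difference is proportional to DE_I + DE_C. The model as written uses DE_I + 1.
- R = true SE / model SE = √[(DE_I + DE_C) / (DE_I + 1)].
- Type I error = 2 × [1 − Φ(1.96 / R)].

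Example with m = 7, ICC 0.05 in both arms and g = 1: DE = 1 + 6 × 0.05 = 1.30; R = √(2.60/2.30) = 1.063; 1.96/1.063 = 1.84; type I error 6.5%.

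Ranges over m = 6 to 8, equal ICC in both arms:

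| ICC | DE | True SE above model SE | Type I, all control fathers grouped | Type I, half grouped |
|---|---|---|---|---|
| 0.02 | 1.10–1.14 | 2.4–3.2% | 5.6–5.8% | 5.3–5.4% |
| 0.05 | 1.25–1.35 | 5.4–7.2% | 6.3–6.8% | 5.6–5.9% |
| 0.10 | 1.50–1.70 | 9.5–12.2% | 7.4–8.1% | 6.2–6.5% |

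**Simulation.** The formula uses a normal reference and known variances, and there are only about 10–13 groups per arm (80/8 = 10; 80/6 ≈ 13). So 40,000 null trials per setting were simulated with 10 groups of 8 or 13 groups of 6 per arm (Monte Carlo error about 0.1 percentage point). The model as written has a group variance in the intervention arm only and a common residual variance. The alternative has a common group variance in both arms. Type I error with equal ICC:

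| Model and reference | ICC 0.02 | ICC 0.05 | ICC 0.10 |
|---|---|---|---|
| As written, Satterthwaite | 5.0–5.1% | 5.7–6.4% | 7.0–7.9% |
| Both arms, Satterthwaite | 4.3% | 4.5–4.8% | 4.8–4.9% |
| As written, z | 5.4–5.7% | 6.3–7.4% | 7.9–9.2% |
| Both arms, z | 4.9–5.1% | 5.4–5.9% | 5.8–6.3% |
| As written, t on 18 or 24 df | 4.2–4.4% | 5.1–5.5% | 6.5–7.2% |

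Further settings, all with Satterthwaite degrees of freedom:

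- Both-arm model with arm-specific group variances: 4.8–4.9% at ICC 0.02–0.10.
- As written, half of control fathers grouped (groups of 8 in the intervention arm): 4.6%, 5.5% and 6.4% at ICC 0.02, 0.05 and 0.10.
- As written, intervention ICC 0.05: 5.1–5.4% if the control ICC is 0.02; 4.7–4.8%, so no inflation, if it is 0.

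**The case against.** The strongest reply is that control groups may hardly exist. The control programme comes by link or website, and its description mentions no follow-up call. The intervention description has four sessions, scheduled viewing times and follow-up calls. Modelling clustering only in the more interactive arm could be defended on that ground. This stands as a reason for uncertainty, but the plan does not make the argument. Links are used in both arms, so if they remove clustering the intervention-arm term loses its basis too.

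Equal ICC is also unfavourable to the plan. The control sessions leave out substance use, violence and HIV, which are the outcomes, and the model adjusts for baseline. The control ICC may therefore be well below the intervention ICC, and the effect shrinks accordingly. Similarity among fathers who join the same group could still produce some correlation.

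Groups may also be smaller than 6–8. Those are numbers invited, and waves of 20 dyads give about 10 per arm, which would split naturally into two groups of 5. At m = 5 the formula gives 5.4%, 6.1% and 7.0% at ICC 0.02, 0.05 and 0.10. Variation shared by both arms of a wave, which was not simulated, would reduce the effect further.

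Part of the excess under a z reference comes from the reference itself, since the both-arm model also exceeds 5% at ICC 0.05 and above. The Satterthwaite rows separate the two effects.

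Finally, the phrase may be loose wording for session groups in general, because the protocol sometimes calls the control programme an intervention. The arm contrast in the same paragraph makes that reading less likely. Section 13 offers only weak support for shared contact among control fathers ("In both treatment conditions, action may be taken by the peer advocate to respond to non-serious events"), and the conclusion does not rest on it.

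**Conclusion.** The concern holds, conditionally as stated. The clustering rule covers one arm of a design that plans groups in both, and it is right only if control fathers do not meet in groups or their group ICC is zero. The documents establish neither.

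The size is modest. With equal ICC, all control fathers grouped and Satterthwaite degrees of freedom, type I error is essentially nominal at ICC 0.02, about 6% at 0.05 and 7–8% at 0.10. It is lower with fewer or smaller control groups or a smaller control ICC. These figures rest on the assumed 1:1 split, 5% level and ICC range, and on continuous outcomes; categorical outcomes were not examined. The wording should be corrected, with medium confidence that the effect will matter in practice.

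**What to change.** Replace the clustering phrase in section 12 with wording to this effect:

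> A random effect for the assigned session group in both arms (arm-specific variances allowed), with Kenward-Roger or Satterthwaite degrees of freedom for continuous outcomes. Fathers who attend no session keep their assigned group. Each dyad that receives the programme only by individual link is its own single-member cluster. The father-son dyad effect is kept.

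Record the assigned session group and the delivery format for every dyad in both arms. The sections available for review do not say that group membership is captured, and without it the control-arm effect may be impossible to model later. A fixed effect for wave could add precision but is optional and not needed to correct this error.

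The cost is analysis-plan wording and two recorded fields. If control groups do not cluster, confidence intervals are about 2% wider (simulated with control ICC 0, intervention ICC 0.05 and a common group variance; the cost with arm-specific variances was not quantified). If they do cluster, intervals widen by the amount needed.
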